 - a. Does the use of GetWell Loop lead to fewer potentially avoidable healthcare utilization encounters such as Emergency Department and hospital visits (including readmissions and reoperations)?
 - b. Does utilizing GetWell Loop improve clinical workflow by minimizing telephone calls and thereby offloading support staff, allowing them to be more efficient?
 - c. Does utilizing GetWell Loop reduce the volume of on call pages by addressing patient questions up front, alleviating concerns, and providing them with the information they need when they need it?
 - d. Does utilizing GetWell Loop allow the practice to identify patients whose inperson follow up needs are minimal, thereby freeing new referrals slots and enhancing same-day access?
 - e. Does GetWell Loop improve the throughput of patients by eliminating unnecessary follow-up appointments?
- 3. Measure length of stay, discharge disposition (home versus extended care facility) and 90 days readmission and reoperation rates
 - a. Does the early detection of adverse signs/symptoms that develop between clinical encounters result in earlier intervention that thereby reduces readmission and reoperations?
 - b. Do Patient Reported Outcomes (PROs), collected at intervals between clinical encounters, provide useful information which facilitates the detections of post-acute complications prior to the next clinical encounter?
 - c. Does patient adherence to instructions as well as recommended activity levels, captured through continuous activity monitoring such as the Jawbone Up Band (a wristband capable of measuring activity), predict time to recovery, functional outcomes, and potential failure rates? (optional)
- 4. Evaluate the financial impact of GetWell Loop in the episode of care

Methods: The study design is a prospective randomized trial in which patients undergoing selected hip and knee orthopedic procedures will be offered peri-operative use of GetWell Loop vs standard care. Approximately 300 patients will be enrolled (150 in each group).

Phase 1: 6 month run-in with 9 month follow (total of 12 month long study). Will collect the following outcome measures:

- Demographics (Age, gender, BMI)
- Comorbidities
- Surgery details (Length of surgery, laterality, surgeon)
- LOS and discharge disposition
- Number/length of follow up visits within 90 days (in person and telephone)
- 90 days readmission and reoperations
- Patient and provider satisfaction survey completion rates

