- Patient satisfaction (VAS scale and PPE-15)

Phase 2: 3 months for statistical analysis and writing manuscript.

Study Participants

- A. Patients Total Hip and Total Knee Arthroplasty patients treated at Avon Hospital
 - a. Inclusion criteria
 - i. Primary THA or TKA patient
 - ii. Personal consent to participate
 - iii. Have internet access or mobile access with a valid email address at the time of enrollment
 - iv. Above the age of 18 and are capable of consent
 - v. English speaking patient
 - b. Exclusion criteria
 - i. Staged arthroplasty procedure within 6 months of the index procedure
 - ii. Abandoned email address of record (e.g. bounce of email from clinic). If so, then data may be censored in the pilot analysis
 - iii. Less than 14 days until scheduled surgery

iv. Outpatient surgery

Data Analysis Plan

The difference in percent of respondents indicating a problem on the PPE-15 between treatment and control groups will be calculated as [percent of standard of care respondents reporting a problem, averaged across all PPE-15 domains] – [percent of GetWell Loop respondents reporting a problem, averaged across all PPE-15 domains], such that a positive difference indicates that the GetWell Loop group was more satisfied than the standard of care group, while a negative value indicates the opposite. A superiority hypothesis test using the two-independent sample t-test will be used to statistically evaluate the difference in the average satisfaction between groups. All other outcomes will be analyzed using chi-square tests for categorical variables and t-tests for continuous variables. Regression analysis will be conducted for multivariate analysis.

Schedule of Events

Evaluation	History	IntraOp	90 days postop	90 days	1 year
	/ PreOp		(Chart Review)	postop	(study completion)
				(survey)	
Demonstration	V				
Demographics	Λ				
Medical	X				
History/Comorbidities					
		V			
Surgical Details		X			
Discharge (LOS, disposition)			Х		
Track				Х	
Readmission/Reoperation					
Track ED visits, office visits				Х	
Track calls and on-call pages				Х	
Adverse Events			Х	Х	
Patient Satisfaction				Х	
VAS and PPF-15					
Provider Satisfaction Survey					Х

Study Metrics

Metric	Justification
Patient satisfaction VAS and PPE-15 (attached)	-Substantial opportunity for the Cleveland Clinic to differentiate itself among health systems and enhance revenue associated with patient satisfaction measures

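### The bounced-email exclusion lets data be dropped at discretion, probably after randomisation, and no as-randomised analysis is stated

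*Combined protocol and SAP*

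**What the plan says.** All locations are in the combined protocol and SAP.

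- **Study Participants, exclusion ii:** "Abandoned email address of record (e.g. bounce of email from clinic). If so, then data may be censored in the pilot analysis".
- **Study Participants, inclusion iii:** "Have internet access or mobile access with a valid email address at the time of enrollment".
- **Study Participants, exclusion iii:** "Less than 14 days until scheduled surgery".
- **Methods:** "The study design is a prospective randomized trial", with about 300 patients, 150 per group.
- **Data Analysis Plan, PPE-15:** the quantity compared is "The difference in percent of respondents indicating a problem on the PPE-15 between treatment and control groups", so this analysis is limited to people who answer the survey.
- **Data Analysis Plan, remaining endpoints:** "All other outcomes will be analyzed using chi-square tests for categorical variables and t-tests for continuous variables", plus regression.
- **Schedule of Events:** length of stay (LOS) and discharge disposition are marked under the 90-day chart review column.

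The document contains no intention-to-treat or other as-randomised statement, no definition of an analysis population and no rule for missing data. It does not say when randomisation takes place relative to enrolment or to a bounce.

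**The concern.** Removing a patient before randomisation leaves the comparison between arms intact. Removing data afterwards, because of something that happened later, can break it. Exclusion ii is listed as an eligibility criterion, but its second sentence governs the analysis.

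The rule is also open-ended. Apart from one example, it does not say what counts as an abandoned address, when the judgement is made, who makes it or which outcomes it affects. *Censored* could mean dropping the patient or only the data after the bounce. The planned t-tests and chi-square tests have no censoring mechanism, so in practice the word means leaving data out.

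Two things are at stake. First, outcomes that need no email, such as LOS and disposition, could be lost for no gain. Second, because the step is optional and undated, it could be taken after results are known, and a reader of the report could not tell.

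**Working it through.** **1. Whom the clause reaches.** An address known to be dead at entry already fails inclusion iii, and there must be data before anything can be censored. The clause therefore works mainly after enrolment. This is an inference from the two criteria read together; the document does not state it.

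**2. How long an address has to fail.** If exclusion iii is applied at enrolment and surgery goes ahead as scheduled, there are at least 14 days before surgery and 90 days of follow-up: 14 + 90 = 104 days.

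**3. What each reading of the clause does to chart outcomes.** If the whole patient is dropped, LOS and disposition are lost whenever the bounce occurs. If only later data are dropped, LOS and disposition survive a bounce after discharge.

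**4. Bias.** Let r be the share of an arm censored, and d the mean of retained minus censored patients in that arm, in SD units. The arm's full mean is (1 − r) × retained + r × censored, so the retained mean differs from it by r·d. The between-arm difference is then biased by

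bias = r1·d1 − r0·d0.

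Equal rates do not remove this unless the gaps are equal too. If d = 0 in both arms, there is no bias.

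**5. Inputs.** The 150 per arm is from Methods. The plan states no alpha, power, SD, bounce rate or outcome gap, so a two-sided 5% test, a true null, and every r and d below are assumptions.

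SE = √[1/(150(1 − r1)) + 1/(150(1 − r0))]

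Type I error = Φ(−1.96 + bias/SE) + Φ(−1.96 − bias/SE)

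Worked case, 5% of one arm with a 1.0 SD gap: bias = 0.05 × 1.0 = 0.05; SE = √(1/142.5 + 1/150) = 0.117; bias/SE = 0.427; type I error = 7.1%.

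| Censored, arm 1 / arm 0 | Gap d1 / d0 (SD) | Bias (SD) | Type I error |
|---|---|---|---|
| 2% / 0 | 0.5 / – | 0.010 | 5.1% |
| 2% / 0 | 1.0 / – | 0.020 | 5.3% |
| 5% / 0 | 0.25 / – | 0.0125 | 5.1% |
| 5% / 0 | 0.5 / – | 0.025 | 5.5% |
| 5% / 0 | 1.0 / – | 0.050 | 7.1% |
| 10% / 0 | 0.5 / – | 0.050 | 7.1% |
| 10% / 0 | 1.0 / – | 0.100 | 13.5% |
| 6% / 2% | 0.5 / 0.5 | 0.020 | 5.3% |
| 6% / 2% | 1.0 / 1.0 | 0.040 | 6.3% |
| 2% / 2% | 1.0 / 0 | 0.020 | 5.3% |
| 5% / 5% | 1.0 / 0.5 | 0.025 | 5.5% |
| 5% / 5% | 1.0 / 0 | 0.050 | 7.1% |
| 5% / 5% | 1.0 / 1.0 | 0 | 5.0% |

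In patients, 2-5% of an arm is 3 to about 8 of 150. Simulated t-tests, 100,000 trials per cell, agreed with the formula in the 2-6% cells with gaps of 0.5 SD or more (for example 7.10% for 5% / 0 at 1.0 SD).

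**6. Scale.** With 150 per arm and 80% power, the detectable difference is 2.80 × √(2/150) = 0.32 SD. A bias of 0.01-0.05 SD is 3-15% of that (0.01/0.3235 and 0.05/0.3235).

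**7. A binary example.** Assume non-home discharge is 20% in retained and 40% in censored patients, with censoring in one arm only. The bias is 0.02 × 20 = 0.4 percentage points at 2% censored and 0.05 × 20 = 1.0 point at 5%. Type I error is 5.1% and 5.5%.

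**8. Precision.** If both arms lose the same share, the SE grows by 1/√(1 − r): 1.010 at 2% and 1.026 at 5%.

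**The case against.** The strongest reply is that nothing shows this bias would be material. The document gives no bounce rate and no reason to expect patients with failed addresses to differ by 0.5-1.0 SD. Most of the 2-5% scenarios leave the type I error between 5.0% and 5.5%; about 7% needs fairly strong assumptions. That stands: the figures show sensitivity and do not estimate this trial's error.

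It also stands that the PPE-15 comparison is already limited to respondents. If that survey goes out by email, which the plan does not say, a patient with a dead address would be missing with or without this clause. Deleting it does not solve survey non-response.

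A third reply is that the clause sits among the exclusion criteria and may only describe how a valid address is verified at entry. The timing is indeed not stated, but this reading does not explain why the text speaks of censoring data in the analysis.

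Finally, an as-randomised sentence would also keep patients later found to meet another exclusion, such as a staged procedure. That is ordinary intention-to-treat practice and does not count against the change. Missing analysis-population wording is a wider gap than the email clause, but here it leaves nothing in the plan to override the optional censoring.

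**Conclusion.** The concern holds and should be fixed. The text is clear on the essentials: censoring is optional, undefined and not limited to outcomes that depend on email, and no as-randomised analysis is stated. That the clause acts mainly on enrolled patients is a sound inference. Whether they are already randomised depends on timing that the plan omits.

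The likely effect is modest if bounces are few, nil if they are unrelated to outcome, and larger only if many patients are censored or the gaps differ sharply between arms. The case for changing the text rests less on the expected size than on the fact that the bias is avoidable and a discretionary exclusion could not be detected afterwards. Chart-based outcomes have the most to lose.

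**What to change.** 1. Delete the second sentence of exclusion ii.
2. Apply the email criterion only before randomisation, in the same way in both arms.
3. Add to the Data Analysis Plan: *Every randomised patient is analysed in the assigned arm using all available outcomes, including chart-based ones, whatever happens to the email address after randomisation.*
4. Report the number of bounced addresses by arm.
5. Label any analysis that leaves out bounced patients as a sensitivity analysis.

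The cost is one deleted sentence, one added sentence, a short timing clarification and a count. The email check at enrolment already exists. Another survey route for patients whose address fails would help but is optional. The downside is slight dilution of the effect by patients the platform could not reach.

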GetWell Loop is a SaaS platform that allows physicians to monitor signs and symptoms, and communicate with patients during the postoperative recovery process. The platform enables doctors to identify patients at risk of decline in the follow up period. Patients are engaged through mobile and web-based surveys, reminders, and information personalized to the patient's specific condition or treatment plan. The company's platform also collects patients' feedbacks and monitors status against expected progress. Alerts are sent to physicians or providers about patients who are at risk of treatment failures, complications, or hospital readmissions. Physicians are informed if patients are trending toward an adverse outcome based on the patient's responses. Along with helping to prevent readmissions, GetWell Loop can also help institutions collect patient-reported outcomes (PROs) data, which can be used to evaluate and improve quality measures.

GetWell Loop and the Cleveland Clinic are interested in collaborating on a clinical pilot study to demonstrate that high patient engagement leads to enhanced pre-operative preparation potentially reducing length of stay (LOS), readmissions / reoperations, discharge disposition to home rather than another facility, reduced need for in-person follow up, increased patient (and provider) satisfaction, and increased satisfaction survey completion rates after elective primary hip and knee arthroplasty (THA and TKA). These improvements can translate on higher financial savings through the episode especially in light of the alternative payment models.

Specific Aims: GetWell Loop is currently used by orthopedic groups around the country, and is believed to improve peri-operative outcomes after THA and TKA and mitigate risk by: 1. Enhancing patient engagement with providers, 2. Allowing patients to play an integral role in patient-reported outcomes, 3. Generating and relaying actionable pre- and post-operative reporting directly to the clinical team, and 4.

Detecting impending post-operative complications early, enabling timely intervention and preventing avoidable complications and readmissions.

The specific aims of this proposal are to:

- 1. Measure the impact of using GetWell Loop on patient (and provider) satisfaction
- 2. Understand the degree to which high post-operative engagement reduces the need for in-person or telephone follow up appointment time

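### The PPE-15 superiority test uses survey respondents only, although GetWell Loop is expected to raise survey completion, and the plan commits to no method for non-response

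*Combined protocol and SAP*

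**What the plan says.** Aim 1, under Specific Aims, reads: "Measure the impact of using GetWell Loop on patient (and provider) satisfaction". For the PPE-15, the Data Analysis Plan subtracts the "percent of GetWell Loop respondents reporting a problem, averaged across all PPE-15 domains" from the matching figure for standard of care respondents, so a positive value favours GetWell Loop. The difference is tested for superiority with a two-independent-sample t-test.

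The Introduction and Background lists, among the effects the study hopes to demonstrate, "increased satisfaction survey completion rates after elective primary hip and knee arthroplasty". Methods, Phase 1, collects "Patient and provider satisfaction survey completion rates" as an outcome.

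Two other sentences in the Data Analysis Plan bear on the point: "All other outcomes will be analyzed using chi-square tests for categorical variables and t-tests for continuous variables", which gives patient survey completion a between-arm chi-square test, and "Regression analysis will be conducted for multivariate analysis", which names neither outcome nor covariates. For an abandoned email address, the exclusion criteria add: "If so, then data may be censored in the pilot analysis".

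No section describes imputation, weighting for non-response, a sensitivity analysis for missing surveys, or an analysis set of all randomised patients.

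**The concern.** Randomisation makes the arms comparable as randomised. It does not make those who answer comparable if treatment influences who answers, and the protocol expects it to. An observed PPE-15 difference could then mix an effect on satisfaction with an effect on who responds. It could produce an apparent advantage for GetWell Loop or hide a real one. The more fully the trial succeeds on its own completion hypothesis, the harder the satisfaction result is to interpret. The VAS is collected at the same 90-day survey point in the Schedule of Events and is exposed in the same way.

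**Working it through.** **Inputs from the documents.** 150 per arm (Methods); respondents-only contrast, standard care minus GetWell Loop, t-test (Data Analysis Plan). The sample size comes with no SD, effect size, alpha or dropout allowance, so it cannot be reproduced and is taken as given.

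**Assumed inputs.** Completion rates, SD 20 points, a 10-point gap between non-respondents and respondents, and a two-sided 5% level. The documents give none of these.

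**Bias.** Let p be completion and d the non-respondent minus respondent mean problem percent. In each arm, respondent mean = true mean − (1 − p)d. The bias in standard care minus GetWell Loop is therefore

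(1 − p_GWL)·d_GWL − (1 − p_SC)·d_SC,

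which reduces to d·(p_SC − p_GWL) when d is equal in both arms.

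**Standard error.** SE = 20·√(1/(150·p_GWL) + 1/(150·p_SC)).

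**Example, 85/65, d = +10, no true effect.** Bias = 10 × (0.65 − 0.85) = −2.0. SE = 20·√(1/127.5 + 1/97.5) = 2.691. The shift is 2.0/2.691 = 0.743 SE. By the normal approximation, the chance of a false result against GetWell Loop is Φ(−1.96 + 0.743) = 11.2% and of one in its favour Φ(−1.96 − 0.743) = 0.3%, a total of 11.5%. With d = −10 the two tails swap.

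| Completion GWL/SC | SE | Bias, d = +10 | Two-sided error, gap 10 | Gap 5 to 15 | Chi-square power for the imbalance |
|---|---|---|---|---|---|
| 85/80 | 2.544 | −0.5 | 5.4% | 5.1–6.0% | 21% |
| 85/75 | 2.587 | −1.0 | 6.7% | not run | 58% |
| 85/65 | 2.691 | −2.0 | 11.5% | 6.6–20.0% | 98% |
| 90/60 | 2.722 | −3.0 | 19.7% | 8.5–38.0% | over 99% |

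At 85/65 with a 10-point gap, SD 15 gives 16.8% and SD 25 gives 9.1%.

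**Equal completion, unequal gaps.** At 80/80, SE = 2.582. Gaps of 10 (GetWell Loop) and 5 (standard care) give bias 0.2 × 10 − 0.2 × 5 = +1.0 and error 6.7%; gaps of 10 and 0 give +2.0 and 12.1%. A chi-square test on completion cannot show this.

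**What a correction achieves.** A simulation of 12,000 trials at 85/65 (d = 10, SD 20 within response group, one covariate with mean 0 in both arms and correlation 0.5 with the outcome, 20 imputations by arm) gave these two-sided errors according to the share of the gap that the covariate explains:

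| Method | None | Half | All |
|---|---|---|---|
| Respondents-only t-test | 11.6% | 11.4% | 11.5% |
| Multiple imputation | 11.6% | 6.5% | 4.9% |
| Response weighting | 12.0% | 6.7% | 6.0% |
| Covariate-adjusted regression on respondents | 13.3% | 6.9% | 5.2% |

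Imputation bias was −2.0, −1.0 and 0.0 points. Its mean SE was 2.63 to 2.77, against 2.69 for the t-test.

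**The case against.** The strongest reply is that the plan already contains useful tools. The chi-square test has 98% power or more in the two scenarios where equal gaps do most harm, and regression is planned. In the simulation, covariate-adjusted regression on respondents did about as well as imputation once the covariate explained half or all of the gap. A reader might infer that the planned methods cannot help, or that imputation is clearly better; neither is supported. What remains is narrower: the regression sentence does not commit to adjusting the PPE-15 for anything. There is also an argument of principle. Adjusting respondents for LOS, disposition or readmission would remove part of any treatment effect, because the Introduction names as expected effects "potentially reducing length of stay (LOS), readmissions / reoperations, discharge disposition to home rather than another facility". An imputation or response model can use those variables without that cost. That advantage was not simulated, since the simulated covariate behaves like a baseline variable.

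Second, the inputs are assumed and some are generous. A 10-point gap is half an SD. With correlation 0.5 and SD 20 the slope is 10 points per covariate SD, so explaining the whole gap needs respondents and non-respondents to differ by a full SD on the covariate. Nothing in the documents suggests that they do. This stands, and it is why a tipping-point analysis is needed.

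Third, the Introduction calls the study a pilot, no outcome is labelled primary, and inclusion requires internet or mobile access and a valid email in both arms, which may limit differential non-contact. That limits how serious the point is. Even so, the PPE-15 is the only outcome given its own test, and being reachable does not ensure a reply. That the listed completion outcome means this survey is an inference, though the natural one from the Schedule of Events.

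**Conclusion.** The point holds as a risk to the Aim 1 estimate that the plan neither corrects nor bounds. Bias arises if completion or the non-respondent gap differs by arm and non-response is related to satisfaction. With equal gaps of 10 points and SD 20, two-sided error is close to nominal for completion differences of 5 to 10 points (5.4% and 6.7%) and reaches 11.5% and 19.7% at differences of 20 and 30 points. It is negligible if completion and gaps are both similar.

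Three stronger readings might be inferred and are not supported. One is that the comparison is biased: the documents give no completion rates or gaps. Another is that the bias favours GetWell Loop: at 85/65, false superiority (nominal 2.5%) is 11.2% if non-respondents report fewer problems but 0.3% if they report more. The third is that the chi-square test would reliably reveal an imbalance: its power is only 21% at 85/80 and 58% at 85/75. Confidence is medium, because every input except the 150 per arm is assumed.

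**What to change.** 1. Keep the respondents-only t-test. Pre-specify beside it, for the PPE-15 and the VAS, an estimate in all randomised patients by multiple imputation or inverse-probability-of-response weighting. Use arm and variables already collected: age, gender, BMI, comorbidities, surgeon, LOS, disposition and 90-day events. Which estimate is labelled main is the sponsor's choice, to be made before arm-level results are seen.
2. Add a tipping-point analysis that varies the non-respondent difference in both directions and separately by arm, and make any superiority conclusion depend on it. No model corrects what the collected variables leave unexplained.
3. Report completion by arm with all randomised patients in the denominator, including those whose email bounces after randomisation.

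The cost is analysis-plan wording and some extra programming, with no new data. The downside is reliance on a response model and a similar or slightly wider interval.

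### The named tests are valid but unadjusted, and the one regression sentence is unspecified; a short, fixed list of pre-operative covariates would be a cheap improvement

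*Combined protocol and SAP*

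**What the plan says.** Methods describes the trial thus: "The study design is a prospective randomized trial". It gives the size as "Approximately 300 patients will be enrolled (150 in each group", with no stratification factors.

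The Data Analysis Plan defines a PPE-15 contrast (control minus GetWell Loop, in percent reporting a problem) and then says, of comparing mean satisfaction across the arms: "A superiority hypothesis test using the two-independent sample t-test will be used". For everything else: "All other outcomes will be analyzed using chi-square tests for categorical variables and t-tests for continuous variables". It closes with: "Regression analysis will be conducted for multivariate analysis". That sentence gives no outcome, model, covariate list, selection rule or status.

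The Phase 1 list in Methods includes "Demographics (Age, gender, BMI", comorbidities, and "Surgery details (Length of surgery, laterality, surgeon". The same list holds LOS, discharge disposition, visits, readmissions and satisfaction. The Schedule of Events places medical history at the pre-operative visit, surgical details intra-operatively, and LOS and disposition at the 90-day chart review. Whether the joint is a hip or a knee is known from the inclusion criteria. Satisfaction is scheduled only at 90 days, so there is no baseline score. No primary endpoint, alpha, power or effect size is stated.

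**The concern.** The trial pools hips and knees and already holds several variables, fixed before surgery, that might explain part of the variation in outcome. A two-sample t-test or chi-square test ignores them. If they do predict outcome, a model that includes them gives a narrower interval for the arm difference from the same patients.

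The regression sentence does not fill this gap, because it supplies no pre-specified estimate for any outcome. It also draws no line between variables known before surgery and those recorded during or after it. LOS and disposition are outcomes under Aim 3, and the Introduction expects the platform to change them. A model that adjusted for them could remove part of the effect being measured. Length of surgery is recorded during the operation, so it is not a baseline variable either.

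**Working it through.** **Inputs from the documents.** About 300 patients, 150 per arm; no covariates in any named test.

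**Inputs assumed because the documents give none.** Two-sided alpha 0.05; 80% power for the unadjusted test; all 300 patients analysed; R² (share of outcome variance explained by the covariates) of 0%, 5%, 10% or 20%; k = 5 or 10 covariate terms.

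**Step 1. The plan's own figure.** The 300 comes with no effect size, SD, alpha or power, so it cannot be reproduced and cannot be called wrong. Inverting the two-means formula at 150 per arm gives a detectable standardised difference of (1.960 + 0.842) × √(2/150) = 0.324. This serves only as the reference point for 80% power.

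**Step 2. Gain before paying for the covariates.** The SE ratio is √(1 − R²): √0.95 = 0.975, √0.90 = 0.949, √0.80 = 0.894. The SE falls by 2.5%, 5.1% or 10.6%.

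**Step 3. Cost of the covariates.** Chance imbalance in k terms inflates the variance of the arm difference by about 1 + k/(300 − 2 − k).

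- Ten terms: 1 + 10/288 = 1.0347; √1.0347 = 1.017, so the SE widens by 1.7%. Break-even R² = 1 − 1/1.0347 = 3.4%.
- Five terms: 1 + 5/293 = 1.0171; √1.0171 = 1.0085, so the SE widens by about 0.9%. Break-even R² = 1 − 1/1.0171 = 1.7%.

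**Step 4. Net result.** Net SE ratio = √[(1 − R²) × inflation]. Power = Φ(2.80/net ratio − 1.96). Equivalent number of unadjusted patients = 300/(net ratio)².

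| Assumed R² | Net SE change, 5 terms | Net SE change, 10 terms | Power, 10 terms | Equivalent N, 10 terms |
|---|---|---|---|---|
| 0% | +0.9% | +1.7% | about 79% | 290 |
| 5% | −1.7% | −0.9% | about 81% | 305 |
| 10% | −4.3% | −3.5% | about 83% | 322 |
| 20% | −9.8% | −9.0% | about 87% | 362 |

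Example for ten terms at R² = 10%: 0.90 × 1.0347 = 0.931; √0.931 = 0.965; Φ(2.80/0.965 − 1.96) = Φ(0.94) = 83%; 300/0.931 = 322.

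**Step 5. Same target.** If all items are answered, the arm mean of each patient's percent of PPE-15 domains with a problem equals the plan's percent averaged across domains. A linear model of that score on arm therefore estimates the contrast the plan already defines.

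**The case against.** The t-test is unbiased under randomisation, and chance imbalance is already allowed for in its error rate. Adjustment is therefore a matter of efficiency, not a correction. That stands.

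Nothing in the documents shows that age, gender, BMI, comorbidity, joint or surgeon predicts PPE-15 problem reports, and there is no baseline score. A gain near zero cannot be excluded. That also stands, and it argues for a short list. The number of surgeons is not given, so surgeon terms could be sparse. The Introduction calls the work a pilot, which lowers the stakes.

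Three stronger readings are tempting, and the documents do not support them:

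- **That precision is demonstrably lost.** This would need a known R², and none is given.
- **That the PPE-15 result can be picked after the data are seen.** If the better of one unadjusted and one adjusted test could be reported, two-sided type I error would be 6.0%, 6.5% or 7.1% at R² of 5%, 10% or 20% (bivariate normal statistics with correlation √(1 − R²)). But the plan says the t-test will be used for that comparison. The open choice is limited to what the regression is for and how much weight it gets.
- **That the plan intends to adjust for LOS, disposition or length of surgery.** It does not say so; it lists them as outcome measures, and nothing in it suggests that the platform alters length of surgery. The gap is only that the regression sentence does not rule them out.

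A reader might also call PPE-15 the primary endpoint. It is the only outcome with its own defined contrast and superiority test, but no primary endpoint is named.

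**Conclusion.** The concern holds as an efficiency and pre-specification point; the named tests are not invalid. The likely gain is small to moderate and the possible loss is small: from a net SE reduction of 9.0% at R² = 20% to a widening of 1.7% at R² = 0 with ten terms, or 0.9% with five. These figures rest on assumed R², alpha and starting power, and on analysis of all 300 patients; the PPE-15 contrast is among respondents, who may be fewer. The need to specify the regression and exclude variables recorded during or after surgery does not depend on R². The change is worth making because the data are essentially in hand and the downside is limited.

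**What to change.** Amend the Data Analysis Plan as follows.

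- **PPE-15.** Make the main analysis a linear model of each patient's problem score on randomised arm, adjusted for a fixed list known before surgery: joint (THA or TKA), age, gender, BMI and a comorbidity count. Add the scheduled surgeon only if there are few surgeons, with sparse levels grouped by a stated rule. Report the difference as control minus GetWell Loop. Keep the t-test as a sensitivity analysis.
- **Other continuous outcomes** (LOS, VAS, visits, cost). Use the same covariates.
- **Binary outcomes.** Use logistic regression with standardised risk differences only above an event-count threshold fixed in advance; below it, leave the comparison unadjusted.
- **Exclusions.** State that length of surgery, LOS and discharge disposition are never covariates.
- **Regression sentence.** Replace it with the above, and label any further modelling exploratory.
- **Definitions.** Fix the comorbidity count and the handling of missing covariates before outcome data are examined.

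The cost is a short rewrite of the analysis section. No new patients are needed. The covariates are already collected or known before surgery; if surgeon is used, it should be the one scheduled at randomisation, not the one recorded intra-operatively.
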